The only proven therapy so far to improve exercise capacity, dyspnea, and QoL in patients with HFpEF is exercise training ³². However, there are two concerns related to exercise training. The first one is the compliance of patients. Secondly, patients with HF have often reduced mobility due to sarcopenia, cachexia or frailty ^{16,33}. Therefore, new interventions and innovations need to be investigated.

Intermittent hyperthermia such as sauna represents a good alternative to the above-mentioned limitations. Moderate Sauna could be equal to low-and moderate-intensity physical exercise training. Heart rate may increase up to 100/min ^{34,35}. In one large (2315 proband) prospective population-based cohort-study in middle-aged men from Eastern Finland with a follow-up of 20.7 years, increased frequency and length of sauna sessions were associated with reduced sudden cardiac death, coronary heart disease (CHD), and fatal cardiovascular disease 36. Some other studies proved improved endothelial function in patients with CHD and HF and shown that sauna is safe in patients with HF and led to improvement of left ventricular ejection fraction and exercise capacity as well as to reduction of natriuretic peptides and arrhythmias ³⁷⁻³⁹. A small study on 6 male distance runners who had one sauna session of 30 minutes twice a week for 3 weeks showed 32% improvement in endurance compared to baseline 40. Furthermore, two 60-minute sessions of whole-body hyperthermia (44°-50° C) and 50% humidity with one week pause showed increased activity of the anabolic cascade in skeletal muscle represented by Akt/mTOR pathway, which is a crucial regulator of skeletal muscle mass 41. Another small interventional study found that daily locally applied heat treatment to skeletal muscle during immobilization period of 10 days in humans prevented the loss of mitochondrial function, increased heat shock protein (HSP), and reduced skeletal muscle atrophy by 37% compared to a sham treatment group 42.

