1.1.2. Exclusion Criteria

- Major cardiovascular event or procedure such as myocardial infarction, percutaneous coronary intervention (PCI), aortocoronary bypass operation in the previous 3 months.
- Patients who have an indication for dual platelet inhibition.
- Stroke.
- Patients who have mechanical heart valves.
- Pulomary embolism.
- Deep vein thrombosis.
- Patients with implanted cardiac devices.
- Severe valvular disease
- Individuals with altered or reduced sweat function, such as in autoimmune diseases, spinal cord injuries, Fabry disease.
- Symptomatic hypotension regardless of the measured value and those with BP systolic <110mmHG
- Patients on oral anticoagulation for other reasons than atrial fibrillation
- Uncontrolled diabetes mellitus (HbA1c>8%), severe renal dysfunction (GFR<30ml/min), or pulmonary disease (COPD GOLD ≥3)
- Primary muscle disorder (e.g. muscular dystrophies)
- Neurological disease (e.g. Dementia, Parkinson)
- right ventricular dysfunction
- uncontrolled arrythmias
- Any condition that in the opinion of the investigator could prohibit performance of 6-MWT.

STUDY PROTOCOL: All participants will undergo a standardized series of assessments as shown in table 1. In case of clinical improvement, these benefits are likely to diminish over time if sauna bathing is discontinued. To address this, patients will be invited for a follow-up visit three months after completing the intervention. All investigations will be repeated, except for the skeletal muscle biopsy.

Table 1: Timetable of the study

	Week 0	Week 1	Week	Week 13	Week 14	Week 30
	Visit 1	Visit 2	2-12	Visit 3	Visit 4	Visit 5
Informed consent	X					
Echocardiography	X			X		X
Cardiopulmonary exercise test (CPET)	X			X		X
6-MWT		X			X	X
Blood tests		X			X	Х
QoL-questionnaire	X			X		X
Accelerometer	X			X		х
isokinetic skeletal muscle measurement	X			X		
Skeletal muscle biopsy		Х			X	
Sauna Intervention (twice weekly)			Х			

METHODOLOGY

Echocardiography: The diameter, size, and function of all 4 chambers will be measured through transthoracic echocardiography. Valve functions as well as the diastolic function will be evaluated. Strain analysis of the left and right ventricle and of the left atrial will be performed as well.

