Proteomics: To further assess molecular changes of the muscle proteome, we will also analyze changes in protein levels of the above-mentioned genes. Total muscle proteins will be obtained using extraction buffer containing sodium fluorate, protease and phosphatase inhibitors without detergent and centrifugation. Samples will be stored at -80°C until the analysis. Protein lysates will be used for the analysis of changes in proteasome content and activity. Also, changes in the expression of specific genes (e.g. myosin heavy chain) will be investigated on the protein level using western blot techniques as previously described ⁵⁸ (**Figure 4**). **Further, we will perform a post-translational modification analyses and global proteome analysis of the entire skeletal muscle proteome.**

[figure not shown]

Figure 4: CPT1B-protein level in patients with HFpEF, HFrEF and in HC measured by western blot. *: p<0.05.

Autophagy: To assess catabolic mechanisms in the skeletal muscle tissue, we will measure LC3I and LC3II using standard western blot techniques and LC3II staining on tissue immunohistology specimens.

Intermittent hyperthermia sessions (sauna):

All participants will be accompanied by medical doctors for two sessions weekly, each between 8-15 minutes. The intervention will be done in the NEMO-sauna in Magdeburg. The duration of the intervention will be 10 weeks. We will start the first 2 weeks with 8 minutes. Week 3-4: 10 minutes, week 5-6: 12 minutes, week 7-10: 12-15 minutes. Sessions will be done in groups each consisting of 5 patients. The temperature of the sauna will be 60°C. After each session a cold shower will follow and then rest for 20 minutes. Blood pressure, heart frequency, O2-Saturation will be measured prior to each session as well as directly after the shower and at the end of the rest.

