9. STATISTICS

There is not enough prior data to calculate the sample size. Our aim is to test primarily the safety of intermittent hyperthermia and the feasibility of the intervention on patients with HF. We still do think based on our previous research and in spite of the small sample volume, that we would find some significant differences in the secondary endpoints comparing baseline data to post intervention.

All data and statistics will be reported as mean \pm standard deviation (n \pm SD) for continuous normally distributed data or as median and interquartile range [25–75%] for variables that were not normally distributed, respectively. Categorical data will be summarized by percentages. The Statistical Package for Social Sciences software (SPSS 26, IBM, Armonk, USA) will be used for statistical analysis. The chi-squared test will be used to look for trend for categorical variables and Kruskal Wallis test will be applied for not normally distributed data, respectively. Analysis of variance (ANOVA), Pearson's or Spearman simple regression will be used as appropriate. A two-tailed p-value <0.05 indicates statistical significance.

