10. ETHICAL ASPECTS OF PROPOSAL

Participation is entirely voluntary and will in no way effect their care. There is no direct benefit to the patients except a strong contribution to science.

All efforts will be made to minimize risk to the subject. The cardiopulmonary test and Biodex muscle function testing will occur in the outpatient clinical area. Emergency equipment and medical personnel will be in the immediate vicinity. Risks associated with skeletal muscle sample collection are very small. Blood samples will be taken during the outpatient visits at low risk. Adverse events will be reviewed on a biweekly basis by a cardiologist otherwise not affiliated with this proposal. Serious adverse events will be reported to the Institutional Review Board within 24 hours. All patient information is kept absolutely confidential.

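### No vital signs are scheduled at the end of the heat, so symptom-free responses to it go unmeasured or are mixed with the effect of the cold shower

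*Protocol*

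**What the plan says.** The sauna paragraph at the end of Section 5 (Methodology, intermittent hyperthermia sessions) describes two sessions a week at 60°C, with doctors accompanying the participants, in groups of five, for 10 weeks. Exposure rises over time: "We will start the first 2 weeks with 8 minutes. Week 3-4: 10 minutes, week 5-6: 12 minutes, week 7-10: 12-15 minutes".

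The order of events is fixed: "After each session a cold shower will follow and then rest for 20 minutes". The timing of the readings is fixed too. Blood pressure, heart rate and O2 saturation "will be measured prior to each session as well as directly after the shower and at the end of the rest".

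The statistics section states the purpose: "Our aim is to test primarily the safety of intermittent hyperthermia and the feasibility of the intervention on patients with HF". The other safety provision is in Section 10: "Adverse events will be reviewed on a biweekly basis by a cardiologist otherwise not affiliated with this proposal". That section also requires serious events to be reported within 24 hours. Table 1 shows only that the sauna takes place; it lists no monitoring within sessions.

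**The concern.** The response that most directly describes tolerance of the heat is the one present when the heat ends. The first reading after the heat is taken only once a second, opposite thermal stimulus has been applied. A fall in pressure or saturation, or a rise in heart rate, that causes no symptoms and has changed by the end of the shower would not appear in the data as it was.

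The protocol itself indicates that these quantities are of interest. The background section says of the heat: "Moderate Sauna could be equal to low-and moderate-intensity physical exercise training. Heart rate may increase up to 100/min". Low blood pressure bars entry: "Symptomatic hypotension regardless of the measured value and those with BP systolic <110mmHG". Exposure is lengthened in steps, yet no step has a reading when the heat stops. At stake is how much the pilot can say about acute haemodynamic tolerance when it is used to plan the larger trial that the protocol foresees.

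**Working it through.** The protocol gives no figure to reproduce on this point. The check is a placement of the readings, a count, and a short argument about what the readings can separate.

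**Inputs.** From Section 5: two sessions a week, 10 weeks, three reading times, 30 patients recruited, at least 12 per group (24) analysed. From Table 1: sauna in weeks 2-12, which is 11 weeks if both ends are counted.

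**1. Placement of the readings.**

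| Point in the session | Reading scheduled? |
|---|---|
| Before the heat | yes |
| During the heat | no |
| End of the heat, before the shower | no |
| Straight after the shower | yes |
| End of the 20-minute rest | yes |

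No other section adds a reading.

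**2. Count.** Sessions per patient = 2 × 10 = 20. Reading sets per patient = 3 × 20 = 60. For 30 patients: 60 × 30 = 1,800; for 24: 60 × 24 = 1,440. On Table 1's 11 weeks: 2 × 11 = 22 sessions, giving 3 × 22 × 30 = 1,980 or 3 × 22 × 24 = 1,584. On either count, the number at the end of the heat is 0. These totals describe the schedule; they do not measure harm.

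**3. By exposure step (10-week schedule, 30 patients, full attendance).**

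| Step | Weeks | Sessions per patient | Patient-sessions | End-of-heat readings |
|---|---|---|---|---|
| 8 min | 1-2 | 2 × 2 = 4 | 120 | 0 |
| 10 min | 3-4 | 2 × 2 = 4 | 120 | 0 |
| 12 min | 5-6 | 2 × 2 = 4 | 120 | 0 |
| 12-15 min | 7-10 | 2 × 4 = 8 | 240 | 0 |
| All | 1-10 | 20 | 600 | 0 |

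**4. What the readings can separate.** Let H be the change from before the session to the end of the heat, and S the change from there to the end of the shower. The first two readings give only H + S: one equation with two unknowns. The reading after rest adds a third unknown, so it does not help.

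**5. How far H + S may lie from H.** The protocol gives no blood pressure data for heat or shower, so everything here is assumed. If pressure falls by D in the heat and the shower reverses a share r of it, the recorded fall is D × (1 − r).

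| r (assumed) | D = 20 mmHg | D = 10 mmHg |
|---|---|---|
| −50% (shower deepens the fall) | 30 | 15 |
| 0% | 20 | 10 |
| 50% | 10 | 5 |
| 100% | 0 | 0 |
| 150% (shower overshoots) | −10, a rise | −5, a rise |

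The recorded change may be larger than, equal to, smaller than or opposite to the change in the heat. Nothing in the protocol says which, and the planned readings cannot tell.

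**The case against.** **The safety aim is not without data on the heat.** This stands. A reader might infer that nothing is recorded about the heat phase, but doctors accompany the sessions and adverse events are reviewed, with serious ones reported within 24 hours. The gap is confined to vital signs in patients without symptoms.

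**The intervention is the whole sequence of heat, shower and rest.** On this view, readings before it and after its parts describe tolerance of what is delivered, and no acute haemodynamic endpoint is promised. Section 4 also makes feasibility the main question. This stands in part: the existing readings are useful and should stay. But Section 9 names safety alongside feasibility as a primary aim, and the state reached within the sequence is part of its safety even if the net change afterwards is small.

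**The direction of any distortion is unknown.** This stands. A reader might infer that the schedule leans towards finding no effect. That would require the shower to reverse the response to heat, and the protocol has no data on this.

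**An end-of-heat reading would not show whether longer heat does more.** This stands too. A reader might infer that the added reading would supply a dose comparison. Exposure length is tied to week for every patient, with no control group, so any difference between steps is mixed with repeated exposure, time and dropout (20% expected). The last step, 12-15 minutes, also overlaps the one before.

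**The background figure and the entry criterion are not hazard limits.** This is correct. The heart rate of up to 100/min is background and the 110 mmHg limit is an eligibility rule. They show that the responses matter to the sponsor, and no more than that.

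**Conclusion.** The point holds in a limited form. Followed as written, the trial takes no vital signs at the end of the heat: 0 of 1,800 scheduled reading sets (0 of 1,980 on Table 1's weeks), at each of the four exposure steps. Symptomatic events are still captured. The symptom-free haemodynamic response to the heat is either unmeasured or inseparable from the shower effect, which limits what can be said under the primary safety aim.

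This conclusion rests on the stated order of events and reading times alone. It needs no assumption about what the shower does. The size of the distortion cannot be given: the illustrative range runs from none to a change of sign. The documents do not support a claim that the safety result is biased in a known direction, or that the trial would otherwise have shown an effect of longer exposure.

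Severity is low. It is worth raising because the timing is fixed at data collection, where no later analysis can repair it, and because the remedy is cheap.

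**What to change.** In the sauna paragraph of Section 5, add one reading time between the first and second: *at the end of the heat, before the shower*. Keep the three existing times. Report the change from before the session to the end of the heat descriptively by exposure step (8, 10, 12 and 12-15 minutes), and state that differences between steps are not attributed to longer heat because step is confounded with week. No hold or stopping limit is proposed.

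**Cost.** One more reading set per patient-session: 20 × 30 = 600, or 22 × 30 = 660 on Table 1's weeks. With 30 / 5 = 6 groups, these are spread over 6 × 20 = 120 or 6 × 22 = 132 group sessions. The doctors and the three measurements are already planned.

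**Downside.** The shower is delayed while the group is read. At an assumed 1-2 minutes per patient and one device, the fifth patient waits for four others, 4-8 minutes, so readings would be taken at unequal delays after the heat. With two devices the fifth patient waits for two rounds, 2-4 minutes. The alternative is to stagger entry as well as exit by the time one reading takes. Staggering exit alone would make exposure times unequal.

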6. PROJECTED PROJECT TIMELINE & FUTURE PLANS

We will be able to begin our study in July 2023. We have previous experience with an established HF population. We expect to reach full recruitment by the end of 2023. Data will be analyzed immediately with focus on presenting initial results in the annual meeting of the German Society of Cardiology and the European society of Cardiology 2024. We expect to have a full analysis for manuscript preparations by the end of 2024.

8. INFORMATION & INFORMED CONSENT

Subjects will sign an informed consent before further inclusion criteria are met.

9. STATISTICS

There is not enough prior data to calculate the sample size. Our aim is to test primarily the safety of intermittent hyperthermia and the feasibility of the intervention on patients with HF. We still do think based on our previous research and in spite of the small sample volume, that we would find some significant differences in the secondary endpoints comparing baseline data to post intervention.

All data and statistics will be reported as mean \pm standard deviation (n \pm SD) for continuous normally distributed data or as median and interquartile range [25–75%] for variables that were not normally distributed, respectively. Categorical data will be summarized by percentages. The Statistical Package for Social Sciences software (SPSS 26, IBM, Armonk, USA) will be used for statistical analysis. The chi-squared test will be used to look for trend for categorical variables and Kruskal Wallis test will be applied for not normally distributed data, respectively. Analysis of variance (ANOVA), Pearson's or Spearman simple regression will be used as appropriate. A two-tailed p-value <0.05 indicates statistical significance.

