In a further related publication [name] et al. found that outpatients with HFpEF had worse QoL and higher anxiety and depression scores compared with HFrEF and non-HF controls. Depression was associated with reduced QoL and was an independent predictor for reduced coordination capacity in these patients ⁴⁹.

Furthermore, we showed recently that novel cardiac markers such as left atrial strain (LAS) might be capable to demonstrate the link between cardiac and peripheral limitations of exercise capacity ⁵⁰. We found in this study in patients with HFpEF and HFrEF that reduced LAS was a sensitive detector for reduced skeletal muscle endurance in these patients with area under the curve AUC (0.8).

Altogether, these data demonstrate that the applicant has ample experience testing exercise function in HF, specifically with cardiopulmonary exercise and skeletal muscle functional testing. Furthermore, the applicant has experience working with muscle tissue and bench science techniques and will be supported by an established group of clinical-translational investigators in the lab of [name].

The next logical step would be to investigate if an intervention such as sauna is safe and if it could reverse these symptoms and manifestations. If this will be proved to be correct, we will plan a larger scale trial.

Our results will likely give a new direction for future research especially in patients with HFpEF This might finally have direct therapeutic implications. We plan as a next step a RCT to confirm our results.

4. AIMS and Hypothesis

The aim of the study is to test the safety and efficacy of intermittent hyperthermia (sauna) in a pilot study on patients with HF. We will compare the results among patients with HFmrEF, and HFpEF regarding cardiac function, exercise capacity, skeletal muscle structure and function, metabolomic changes, cognitive function and quality of life both at baseline and after the intervention with sauna.

Hypothesis: We hypothesize that intermittent hyperthermia (sauna) is a feasible intervention in patients with HF regardless of LVEF. Exploratively we will test the effect of the intervention on filling pressure (E/é) as well as on the level of NT-pro-BNP. Peripherally, skeletal muscle function (including metabolic and mitochondrial function) and structure. Finally, the effects of the intervention on QoL and of cognitive function will be tested.

Questions to be answered through our investigation, and how:

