5. RESEARCH DESIGN & METHODOLOGY

Study Population: HF patients will be recruited from in the clinic of cardiology and angiology in the University Hospital in Magdeburg. The HF outpatient clinic includes a diverse group of both men and women; therefore, study subjects will not be limited by gender. Altogether, 30 patients, 15 in each group will be recruited prospectively and will enter the final analysis. At least 12 patients per group will be analysed with an expected drop-out-rate of 20%. Stratifications will be performed regarding sex and age to guarantee similar distribution in and among these groups.

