Serum analyses: Serum will be obtained from all individuals at the time of CPET and muscle biopsy, to assess changes in serum biomarkers. Standard phlebotomy technique in sterile fashion will be utilized. Serum samples will be analyzed for several biomarkers (IGF-1, myostatin, insulin, growth hormone) which will complement the skeletal muscle assessments. We will use western blot techniques ⁵⁸ and commercially available ELISA kits (R&D, USA).

Metabolomic analysis and Lipidomics:

Altogether 188 metabolites (ACs, AAs, biogenic amines, glycerophospholipids, sphingolipids, and sugars) will be quantified in serum using the AbsoluteIDQTM kit p180 (Biocrates Life Science AG, Innsbruck, Austria). The measurement will be performed after exercise (CPET) both in skeletal muscle and serum, and at rest in serum (Figure 3). Circulating fatty acids and ceramide levels will be analyzed in both the serum and skeletal muscle using LC/MS lipidomics. Total lipids will be isolated using the Forch method. Analysis will be performed in collaboration with the Institute of Clinical Chemistry ⁴⁷.

[figure not shown]

Figure 3: Metabolomic profiles of patients with reduced muscle endurance (RME) vs. preserved muscle endurance (PME) in HFpEF vs. HFrEF suggest different distorted metabolites and likely different mechanisms and metabolic pathways accompanying the RME. Visualization of the metabolomic profile using heat maps to show changes in the top 25 metabolite concentrations, and partial least squares-discriminant analysis (PLS-DA) among HFpEF ((A), A-1 and A-2), HFrEF ((B), B-1 and B-2), and in patients with RME and HFpEF vs. RME and HFrEF ((C), C-1 and C-2), respectively ([name] et al. Cells 2022).

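### Section 9 lets observed normality choose each variable's summary and test; at 12 to 15 patients per group that choice is unstable, and it costs some before-after precision for NT-proBNP

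*Protocol*

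**What the plan says.** Section 9 (Statistics) gives one rule for continuous variables. They are reported as mean and SD "for continuous normally distributed data or as median and interquartile range" when they are not normal. On tests it states that "Kruskal Wallis test will be applied for not normally distributed data"; ANOVA and Pearson or Spearman regression are to be used where suitable. It gives no criterion for normality and mentions no transformation. It also states "A two-tailed p-value <0.05 indicates statistical significance" and, on size, "There is not enough prior data to calculate the sample size".

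The numbers are in Section 5 (Study Population): "Altogether, 30 patients, 15 in each group will be recruited prospectively", and "At least 12 patients per group will be analysed with an expected drop-out-rate of 20" per cent.

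Section 4 (Aims and Hypothesis) names the effect of sauna on filling pressure "as well as on the level of NT-pro-BNP" as exploratory. Section 5 (Serum analyses) adds further concentrations: "Serum samples will be analyzed for several biomarkers (IGF-1, myostatin, insulin, growth hormone". Section 9 expects some significant secondary findings, and expects them from comparing values before and after the intervention.

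**The concern.** The rule lets a property of a small sample decide how a variable is described and tested. In 12 to 15 values a normality check has little power, so a skewed marker may land on either side by chance.

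For a marker that is right-skewed and changes by a proportion, neither outcome serves the before-after question well. A t-test on differences in measured units is dominated by the few patients with high values. A signed-rank test on those differences does better but still weights patients by their absolute level. The ratio of post to pre within each patient removes that dependence.

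At stake is some precision in a sample of 24 to 30, and a result that is hard to reuse. The pilot is meant to support planning a larger study, and a geometric mean ratio with its interval serves that directly.

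**Working it through.** **Inputs from the protocol.** Section 5: 15 recruited per group, 20% dropout, at least 12 analysed. 15 × (1 − 0.20) = 12, so these figures agree; both groups together give 24 to 30. Section 9: two-sided 0.05. No effect size, SD or power is stated, so there is no power figure to reproduce.

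**Assumptions, not in the protocol.** Lognormal marker with log-SD s of 0.5, 0.8 or 1.0; within-patient correlation ρ of 0.8 to 0.9; true fall of 20%; Shapiro-Wilk at 5% standing in for the unnamed check. Section 9 names no paired test. The rule is given the benefit of one: paired t if normal, Wilcoxon signed-rank if not, on measured values. Results are simulated. With 2,000 samples the standard error of a power near 50% is √(0.5 × 0.5 / 2,000) = 1.1 points.

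**Step 1: stability of the classification.** If p is the chance that a sample is flagged non-normal, two groups from the same distribution are classed differently with probability 2p(1 − p). For p = 0.57 this is 2 × 0.57 × 0.43 = 0.49, as simulated.

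| s | Flagged, n=12 / 15 | Two groups differ, n=12 / 15 | Baseline and post differ (ρ = 0.85), n=12 / 15 / 24 / 30 |
|---|---|---|---|
| 0.5 | 29% / 38% | 42% / 47% | 25.6 / 29.3 / 30.5 / 27.5% |
| 0.8 | 57% / 70% | 49% / 42% | 33.4 / 30.0 / 12.3 / 6.5% |
| 1.0 | 70% / 84% | 42% / 27% | 30.7 / 22.5 / 5.4 / 1.6% |

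**Step 2: power for the before-after comparison.** The SD of the log ratio is s√(2(1 − ρ)), and the noncentrality is |ln 0.8| × √n / SD. For s = 0.8, ρ = 0.8, n = 24: SD = 0.8 × √0.4 = 0.506, and noncentrality = 0.223 × 4.899 / 0.506 = 2.16. Against a critical t of 2.07 (23 df), power is a little over one half, which agrees with the simulated 53% to 56%.

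Rule against log ratio at n = 24, 20% fall, normality judged at each visit:

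| s | ρ = 0.8 | ρ = 0.9 |
|---|---|---|
| 0.5 | 87 v 92% (5 points) | 99 v 100% (1) |
| 0.8 | 47 v 56% (9) | 75 v 83% (8) |
| 1.0 | 33 v 40% (7) | 54 v 64% (10) |

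Judging normality on the differences instead gives, at ρ = 0.8, 45 v 54% (s = 0.8) and 30 v 38% (s = 1.0); at ρ = 0.9, 73 v 82% and 53 v 64%. The losses are 8 to 11 points. Over the whole range of assumptions the loss is about 0 to 11 points at n = 24 and 3 to 11 at n = 12.

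A separate run at n = 12 with a 25% fall gave 58.5 v 63.9% (s = 0.5, ρ = 0.70), 43.9 v 53.7% (0.8, 0.85) and 26.9 v 36.8% (1.0, 0.85), that is, losses of 5.4, 9.8 and 9.9 points.

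**Step 3: where nothing is lost.** Comparing levels between groups at one visit, with a twofold difference, rule against log scale: at n = 12, 52.3 v 52.7% (s = 0.8) and 36.8 v 36.8% (s = 1.0); at n = 15, 63.2 v 64.2% and 44.6 v 46.3%. Ranks of levels do not change when logs are taken.

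**Step 4: type I error.** It was about 4% to 6% for both the normality-driven choice and the log-ratio analysis.

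**The case against.** The strongest reply is that Section 9 is silent rather than wrong. It never says that data stay untransformed, and scale and normality criteria are commonly left to an analysis plan, which is not at hand. This stands in part: the measured scale is inferred from the absence of any transformation. But the section does state a rule, and an analysis plan that follows it inherits the weakness. If such a plan already fixes the log scale for NT-proBNP, all that remains is to align the protocol.

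Second, the skewness, log-SD, correlation and proportional effect are all assumed, and under a lognormal model with a proportional effect the log analysis is favoured by construction. This stands, and it is why the size is given as a range that starts at zero.

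Third, the comparison uses paired tests that Section 9 does not name. That is also true. The absence of a named paired test is a separate and larger issue; the loss described here would remain after it was cured.

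Fourth, the two harms do not peak together. At n = 24 the classification is fairly stable for log-SD 0.8 to 1.0, where the power loss is larger. It is unstable at 0.5, where the loss is smallest. This stands for pooled analyses; at 12 to 15 per group the instability is present throughout.

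Finally, the stakes are limited. Safety and feasibility are primary, and no power is claimed for any biomarker.

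**Conclusion.** The point holds at low to moderate importance. For a roughly lognormal NT-proBNP, the normality-driven rule is unstable at 12 to 15 per group. It trails a paired log-ratio analysis by about 3 to 11 points of power at n = 12 and 0 to 11 at n = 24, under the assumptions listed. Type I error is not a concern.

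A reader might infer more than the documents support:

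- **A loss of 15 to 28 points.** This comes from setting the raw paired t-test alone against the log ratio at n = 24 (38 v 53%, and 37 v 65%). The rule would rarely take that branch for strongly skewed data at that size.
- **That every branch works on the weaker scale.** Kruskal-Wallis and Spearman applied to levels give the same answer with or without logs.
- **That a marker will be shown as a mean at one visit and a median at the other.** This needs normality to be judged visit by visit, whereas Section 9 words its rule by variable. It is possible, not stated.
- **That every concentration and expression measure should be logged.** The protocol gives neither distributions nor scales for the metabolite, lipid, mRNA and protein measures, so so broad a rule has no basis in it.

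**What to change.** Add to Section 9:

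> NT-proBNP is analysed on the log scale regardless of a normality test. The effect is the within-patient log ratio post/pre, reported as a geometric mean ratio with 95% CI. Other serum concentrations expected to be right-skewed are listed in advance and handled the same way. For all other variables the distribution is judged once, on the within-patient change, and the same summary is used at every visit.

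The cost is these few sentences and a short list of markers. Effects on the log scale read as percent change, and values below the detection limit need a substitution rule, stated in advance. The wording also settles pairing for NT-proBNP and the listed markers. For the other endpoints a paired or baseline-adjusted method still has to be named separately.
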